
Objectives

The primary objective is to test the feasibility of treating chronic pain with yoga delivered via telehealth. We will modify an existing yoga intervention for chronic musculoskeletal pain and address the technical challenges of at-home teleyoga. Then, using the modified intervention, we will demonstrate the feasibility of conducting a randomized controlled trial involving at-home teleyoga.

Specific Aims and Hypothesis

Specific Aims:

1. Modify an existing yoga intervention for chronic musculoskeletal pain and address the technical challenges of at-home teleyoga.
2. Demonstrate the feasibility of conducting a randomized controlled trial involving at-home teleyoga.

Hypothesis 1 (primary): a) Treatment satisfaction as measured by the Multi-Dimensional Treatment Satisfaction Measure will be neutral or positive for all factors. B) Treatment satisfaction will be at least neutral for all items.

Hypothesis 2 (secondary): a) It will be feasible to recruit 30 participants over a 3-month period and deliver yoga in-person or via at-home teleyoga while maintaining a retention rate commensurate with other similar studies. b) Fidelity of treatment delivery will be acceptable as measured by scoring of taped sessions. c) We expect participants will complete the PROMIS measures with a missing data rate not to exceed 15% per participant. d) The yoga intervention will be safe with no serious adverse events in either treatment group.

Study Design

This study aims to investigate the feasibility of at-home teleyoga for veterans with chronic musculoskeletal pain. We will demonstrate the feasibility of conducting a randomized controlled trial involving at-home teleyoga. We will randomize veterans (N=30) with chronic musculoskeletal pain to at-home teleyoga or in-person yoga. Primary feasibility outcomes will include recruitment rates, retention, protocol adherence, participant satisfaction from semi-structured questionnaires, adverse events, treatment fidelity, and rates of completion of study instruments. Feasibility will be determined by comparison to benchmarks from studies that used similar interventions and populations.

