We intend to recruit local (residing in the San Francisco Bay Area), outpatient adult veterans with chronic musculoskeletal pain to enroll in this clinical trial. This research proposal will use randomization after baseline assessments to assign participants (n=30) to at-home teleyoga or in-person yoga (n=15 per group). Randomization will occur by identifying group membership in 30 sealed envelopes and having each participant draw one envelope. To be representative of the veteran population at VAPAHCS Health Care System (VAPAHCS) each group will have 1-2 females.

All human subjects research will be performed at VAPAHCS in Palo Alto, California or at the homes of the veterans (residing in the San Francisco Bay Area) who receive the at-home teleyoga group. There are no other collaborating sites where human subjects research will be performed.

Month					
1	2	3	4	5	6
Recruit (n=30)			Run in-person yoga groups (n=15) Run at-home teleyoga groups (n=15)		

Table 1. Recruitment Table

Group assignment and randomization

Eligible participants will be added to a cohort list; when 30 have been identified, the study team will schedule baseline assessments. After the baseline assessments, participants will be randomized to in-person or at-home teleyoga (n=15 per group). Randomization will occur by identifying group membership in 30 sealed envelopes and having each participant draw one envelope. Each group will contain 1-2 females, to be representative of the veteran population at VAPAHCS.

Statistical Plan and Data Analysis

Fidelity and Missing Data Benchmarks

Fidelity: The instructors will review the video recorded sessions using a manual checklist for instructor adherence to the yoga manuals, which will consist of a Yes/No for each procedure or instruction.

Missing Data: Like similar behavioral outcome measures, we expect missing data in the PROMIS-PI measures not to exceed 15%.

The main analytic strategy will be descriptive statistics at pre- and post-intervention assessments in each arm. We will then preliminarily compare the two conditions in line with the intention to treat principle. The purpose of these comparisons is not to provide formal inference but provide preliminary information to guide the adequately powered future trial.

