Potential participants (n=30) will be invited to the VAPAHCS for a screening visit. The Project Manager will obtain informed consent and review the Health Insurance Portability & Accountability Act (HIPAA) document. After obtaining informed consent, a trained researcher will collect demographic information (Demographic Questionnaire). Screening for protocol eligibility will include the Clinical Questionnaire and DVPRS.

Study Assessments

Demographics Questionnaire: Documents age, gender, education, and race/ethnicity.

Clinical Questionnaire: Self-report document focusing on the existence of 78 health symptoms taken from a list of ICD-9 codes that are highly likely to represent chronic pain.

Medication Use: Self-report of all current pharmacological and non-pharmacological treatments.

Yoga Home Practice Log: Log for participant to document their yoga home practice on non-treatment days.

BDI-II Beck Depression Inventory-II (BDI-II): Contains 21 self-report questions, scored on a 0-3 scale, related over the past two weeks to sleep, appetite, punishment, suicide, and interest in sex.

Brief Pain Inventory-Short Form (BPI-SF): Assesses intensity and impact of pain on functioning on a 0-10 rating scale. Interference is assessed on daily life (general, walking, work, mood, enjoyment, relationships, sleep). The BPI is recommended by the Initiative on Methods, Measurement, and Pain Assessment in Clinical Trials (IMMPACT) group for inclusion in clinical trials evaluating pain.

Defense and Veterans Pain Rating Scale (DVPRS): A five-item scale: one 0-10 pain intensity numeric rating scale and four supplemental items measuring functional outcomes (general activity, sleep, mood, level of stress). The pain intensity scale is designed to improve upon existing scales by using visual cues and word descriptors to anchor pain ratings with perceptual experiences and limitations imposed by pain.

PEG: A 3-item pain measure derived from the Brief Pain Inventory and validated in ambulatory care settings. It includes 1 severity item (average pain) and 2 interference items (enjoyment of life and general activity).

Patient-Reported Outcomes Measurement Information System-Pain Interference

(PROMIS-PI) (108): Examines the extent to which pain hinders engagement over the past seven days with social, cognitive, emotional, physical, recreational activities, and physical functioning through Likert-type 1-5 scales.

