Treatment Satisfaction: Assessed using the Multi-Dimensional Treatment Satisfaction Measure (MDTSM). The measure consists of 11 subscales assessing treatment process and outcome attributes. Each subscale has 1-8 items (see Table 5). Each question except the Discomfort subscale is rated on a five-point scale ranging from “not at all (0)” to “very much (4)”. Thus, a score of 2 represents a rating of neutral satisfaction. The instrument was developed for behavioral interventions and is designed to provide a comprehensive set of treatment attributes to consider when evaluating treatments in the context of pilot studies. It is designed to be completed after exposure to an intervention, to point to aspects of treatments that are viewed favorably or unfavorably. The MDTSM is relevant to many types of behavioral interventions and can be tailored to our yoga intervention. The MDTSM subscales demonstrates good internal consistency, reliability, and validity.

	Data Collection			
	Screening	Baseline	Yoga (wks 1-12)	Post-treatment
Background				
Consent Form	×			
Demographic Questionnaire	×			
Clinical Questionnaire	×			
Yoga Medical Clearance Form	×			
Medical Use		×		×
Yoga Home Practice Log			×	
Mental Health				
BDI-II		×		×
Pain/QOL/Physical				
BPI-SF		×		×
DVPRS	×			
PEG	×	×		×
PROMIS-PI		×		×
Behavioral				

Treatment Satisfaction				x
Provider Suggestions				x
Patient Safety			x	x
Treatment Fidelity			x	

Table 2. Study Measures and Timetable of Data Collection

Yoga Treatment

Participants will be randomized to in-person yoga (n=15) or online yoga (n=15). Yoga classes will be 75-minutes and will be delivered by a yoga instructor once a week over a course of 12 weeks in-person or online.

Yoga (in-person): Veterans in the in-person yoga group will attend yoga classes at VAPAHCS. The yoga instructor will provide weekly instruction at the VAPAHCS in a telehealth-equipped conference room.

Yoga (online): The yoga instructor will provide weekly instruction using approved teleconferencing software either from an offsite location or from the VAPAHCS in a telehealth-equipped conference room.

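### Fidelity is scored by the yoga instructors, with nothing to stop an instructor from rating the classes they taught, so the figure is open to upward bias of unknown size

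*Combined protocol and SAP*

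**What the plan says.** All references are to the combined protocol and SAP.

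- **Who rates.** Statistical Plan and Data Analysis, Fidelity and Missing Data Benchmarks: "The instructors will review the video recorded sessions using a manual checklist for instructor adherence to the yoga manuals". The checklist is binary: "which will consist of a Yes/No for each procedure or instruction".
- **Who is rated.** Yoga Treatment: the classes "will be delivered by a yoga instructor once a week over a course of 12 weeks in-person or online".
- **The criterion.** Specific Aims and Hypothesis, Hypothesis 2b, labelled secondary: "Fidelity of treatment delivery will be acceptable as measured by scoring of taped sessions".
- **Its standing.** Study Design: "Primary feasibility outcomes will include recruitment rates, retention, protocol adherence, participant satisfaction from semi-structured questionnaires, adverse events, treatment fidelity" and completion of instruments. The yardstick given there is general: "Feasibility will be determined by comparison to benchmarks from studies that used similar interventions and populations". No benchmark value for fidelity is stated. The other item under the benchmarks heading, missing PROMIS-PI data, has a limit of 15%.

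The plan describes no rater from outside the teaching role, no second rating, no agreement check and no allocation of raters to sessions.

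**The concern.** The checklist measures whether instructors kept to the manual, and instructors fill it in. Someone scoring a class they taught knows what they meant to do, knows the arm, and has an interest in the result. The natural direction of error is to credit a step that was skipped or cut short.

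The study is meant to show that a modified, at-home version of the intervention can be delivered in a randomized trial, and to inform a larger one. If departures from the manual in the online format are scored leniently, the next trial inherits a delivery problem that the recordings could have revealed. Because the sessions are recorded anyway, a more independent score is within reach.

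**Working it through.** **1. Is there a figure to reproduce?** No. The plan gives no fidelity threshold, expected score or agreement statistic, and no formal inference is planned. The check is therefore a reading of the text, followed by an illustration on assumed values.

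**2. Reading the text.** Fidelity and Missing Data Benchmarks uses the plural for the raters. Yoga Treatment uses the singular for the person teaching. Neither states how many instructors there are or who scores which recording.

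| Staffing | What the current wording allows |
|---|---|
| One instructor | Every session is self-scored |
| Two or more | Self-scoring, peer scoring or a mixture |

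In each case rater and rated hold the same role. Self-scoring is permitted rather than stated.

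**3. How far could lenient scoring move the result?** Let p be the true share of checklist items delivered and f the share of omitted items marked Yes. Both are assumptions. Then

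recorded fidelity = p + (1 − p) × f.

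- p = 0.75, f = 0.10: 0.75 + 0.25 × 0.10 = 0.775
- p = 0.75, f = 0.40: 0.75 + 0.25 × 0.40 = 0.85
- p = 0.70, f = 0.25: 0.70 + 0.30 × 0.25 = 0.775
- p = 0.70, f = 0.50: 0.70 + 0.30 × 0.50 = 0.85

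The leniency needed to reach a threshold T is f = (T − p)/(1 − p). T is also assumed, since the plan gives none.

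| Assumed T | True p | f needed |
|---|---|---|
| 80% | 70% | 0.10/0.30 = 33% |
| 80% | 60% | 0.20/0.40 = 50% |
| 90% | 85% | 0.05/0.15 = 33% |
| 90% | 80% | 0.10/0.20 = 50% |
| 90% | 70% | 0.20/0.30 = 67% |

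Moderate to heavy leniency could carry a result across a plausible threshold. Nothing in the plan says whether such leniency would occur.

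**4. Effect on a comparison of arms.** If f is the same in both arms, the recorded difference is (1 − f) times the true difference. For f between 10% and 40%, 90% to 60% of the difference remains, in the same direction. If f differs, a false difference can appear: with p = 75% in both arms and f of 10% in one and 40% in the other, the scores are 77.5% and 85%, a gap of 7.5 points. The plan gives no information on which case applies.

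**5. Cost of a second rating.** Classes last 75 minutes (1.25 hours), weekly for 12 weeks, in two arms. With one class per arm per week there are 12 × 2 = 24 sessions. A 25% sample is 6 recordings, or three per arm, and 6 × 1.25 = 7.5 hours of playback. Table 1 speaks of groups in the plural. With two classes per arm per week the figures would be 48 sessions, 12 recordings and 15 hours.

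**The case against.** **The plural may mean peer review.** The text fits instructors scoring one another as well as it fits self-scoring, so swapping may already be the intention. This stands: a reader might infer that the plan prescribes self-scoring, and it does not. What remains is that nothing rules it out and that one instructor would leave no alternative.

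**The criterion cannot be shown to be met through bias.** A reader might infer that an acceptable result is likely because of who scores it. That does not follow. *Acceptable* has no number attached, the values of p, f and T above are assumed, and the documents do not measure leniency. Item-level Yes/No marks made from a recording also leave less room for discretion than a global or recalled rating, and can be audited later.

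**Hypothesis 2b does not compare arms.** A reader might take it to ask whether online delivery follows the manual as closely as in-person delivery. It asks only whether fidelity is acceptable. Equal leniency would also shrink a difference between arms without erasing it. Reporting by arm is useful because the plan describes each arm, not because Hypothesis 2b requires it.

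**Weight.** Hypothesis 2 is secondary, fidelity plays no part in the primary hypothesis on satisfaction, and in a 30-person pilot the use of instructors as raters is partly a matter of resources. This limits the seriousness of the point. It does not remove it, because Study Design lists fidelity among the primary feasibility outcomes.

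**A small outside sample should not replace full review.** This stands. Three recordings per arm could miss drift over 12 weeks. The Project Manager and trained researcher are described only in connection with consent, screening and demographics, so their knowledge of the yoga manual cannot be assumed.

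**Conclusion.** The point holds in a limited form. Instructors score instructor adherence, self-scoring is not excluded, and no independent check is described. The fidelity result is therefore open to upward bias, and its size is unknown. The 77.5% to 85% range for a true 75% rests wholly on the assumption that 10% to 40% of omitted items are credited, and shows only that the effect need not be trivial.

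The missing threshold works in two directions. It prevents any claim that bias decides the outcome, and it leaves Hypothesis 2b without a pass rule even under better scoring.

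The change is worth making because fidelity is a listed feasibility outcome and the recordings already exist. Sample size, error rates and the primary hypothesis are unaffected.

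**What to change.** **If there are two or more instructors.** State that no session is scored by the person who taught it. Instructors swap the existing recordings and use the same Yes/No checklist. The viewing time is the time already planned.

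**If there is only one instructor.** Keep that instructor's scoring of all sessions and label it self-rated. Have an existing study-team member who is familiar with the manual score a random subset in each arm, for example one recording from each four-week block, which gives three per arm with one class per week. Report both figures and their item-level agreement, including how often the instructor marked Yes where the second rater marked No. That last share gives a direct, if imprecise, indication of leniency.

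**In either case.** Report the percent of checklist items delivered, by arm. Stating in advance what percentage counts as acceptable would give Hypothesis 2b a decision rule.

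**Cost.** Swapping costs almost nothing. The single-instructor option takes about 7.5 hours of playback for six recordings (more if there are several groups per arm), plus brief familiarisation of the second rater and the small added step of drawing the sample. The reported fidelity may be lower. Treatment, sample size and participant burden do not change.

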The estimated changes and their group differences in pain and depression measured by the BPI-SF and BDI-II will provide preliminary data on target engagement and therefore inform and shape the future trial in terms of elucidating the mechanism of action. We will make a rigorous effort to minimize missing data. Nonetheless, we expect some attrition by post-intervention assessment. For group comparisons, we will focus on collecting preliminary data on clinical significance (i.e. effect size), instead of making formal inference (i.e., *p*-value).

Inclusion/Exclusion Criteria

Identify inclusion criteria.

- Veteran of the United States Armed Forces ≥ 18 years old
- Diagnosis of chronic musculoskeletal pain > 6 months (Dworkin, 2012)
- Minimum pain intensity at screening visit: pain rated ≥ 4 on a 0-10 Numeric Rating Scale (NRS) as recommended by IMMPACT guidelines. We intend to use the NRS from the Defense and Veterans Pain Rating Scale (DVPRS).
- Has not begun new pain treatments or medications in the past month.
- If on a psychotropic medication regimen: stable regimen for at least 4 weeks prior to entry to the study; willingness to remain on a stable regimen during the 12-week acute treatment phase.
- English literacy.
- Wireless internet connection at home.

Identify exclusion criteria.

- Participation in another concurrent clinical trial.
- Back surgery within the last 12 months.
- Back pain potentially attributed to a specific underlying cause, disease, or condition.
- Baseline pain < 4 or ≥ 9 on a 0-10 Numeric Rating Scale (NRS) as recommended by IMMPACT guidelines. We intend to use the NRS from the Defense and Veterans Pain Rating Scale (DVPRS). For ratings ≥ 9 , we will refer the veteran to the provider for prompt care.
- Unstable, serious coexisting medical illness.
- Unstable, serious coexisting mental illness or psychiatric conditions.
- practiced yoga ≥ 1 x in the past 12 months
- Active current suicidal intent or plan.

Criteria will be applied based on the informed consent process, a review of the participant's VA electronic medical record (EMR) and a screening interview.

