The study will exclude participants with back pain potentially attributed to specific underlying causes, diseases, or conditions (e.g. pregnancy, previous back surgery, fractures, dislocations); unstable, serious coexisting medical illnesses (e.g. Congestive Heart Failure, cancer, COPD, dementia); unstable, serious coexisting mental illnesses or psychiatric conditions (e.g. unmanaged psychosis, active substance abuse); or minimal or maximal pain ratings at the time of screening (<4 or \geq 9 on a 0-10 Numeric Rating Scale (NRS) as recommended by IMMPACT guidelines). We intend to use the NRS from the Defense and Veterans Pain Rating Scale (DVPRS).

Participants on a psychotropic medication regimen will be asked to maintain a stable regimen for at least four weeks prior to entry to the study and remain on a stable regimen during the 12-week acute treatment phase, under the patient's medical care team. Excluded participants will be reconsidered for eligibility after stability on medication is achieved. Involvement in medical treatments will be tracked closely through self-report and clinician interviews, and we will use this information when analyzing the results. Participants with active current suicidal intent or plan will be excluded. Participants at risk for suicide will be required to establish a written safety plan involving their primary psychiatrist and the treatment team, prior to entering the clinical trial.

All participants will be able to read, verbalize understanding, and voluntarily sign the Informed Consent and Health Insurance Portability & Accountability Act (HIPAA) prior to the performance of any study-specific procedures or assessments.

Since we seek to assess the feasibility of providing at-home teleyoga via VA Video Connect, all participants will need access to wireless internet connection at home.

Informed Consent Process

Veterans will be recruited from three sources: the VAPAHCS Pain Clinic, local advertising, and web-based advertising. These sources will result in either 1) the potential participant calling the study team or 2) with the participant's consent, the study staff contacting them directly. Study candidates will be invited to the VAPAHCS for a screening visit, during which the Project Manager will obtain informed consent and review the Health Insurance Portability & Accountability Act (HIPAA) document.

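### The plan names intention to treat and expects dropout, but states no baseline adjustment and does not say who enters each time point, so its change estimates may carry a modest, avoidable bias

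*Combined protocol and SAP*

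**What the plan says.** Under Statistical Plan and Data Analysis:

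- The core of the analysis: "The main analytic strategy will be descriptive statistics at pre- and post-intervention assessments in each arm".
- The comparison that follows: "We will then preliminarily compare the two conditions in line with the intention to treat principle".
- The quantity of interest: "The estimated changes and their group differences in pain and depression measured by the BPI-SF and BDI-II will provide preliminary data on target engagement". No estimator is named.
- On missing data: "We will make a rigorous effort to minimize missing data", and then "Nonetheless, we expect some attrition by post-intervention assessment". No dropout rate, analysis set, imputation, model or sensitivity analysis is given. The 15% figure in the same section is a completion benchmark for PROMIS-PI, not a dropout rate for BPI-SF or BDI-II.
- Formal inference is disclaimed, and the results are to be effect sizes that guide a later, powered trial.

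The narrative under Inclusion/Exclusion Criteria adds: "Involvement in medical treatments will be tracked closely through self-report and clinician interviews, and we will use this information when analyzing the results". Table 2 schedules the treatment-use form at baseline and post-treatment, so the data will include information collected after randomisation.

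**The concern.** Intention to treat concerns every randomised participant. Once some have no post score, the label alone does not fix an analysis, because someone must decide what to do about those participants. The plan leaves that decision open, so it could be made after the data are seen.

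Two simple readings are available. One compares the pre mean of everyone with the post mean of those who stayed. The other takes within-person change in those who stayed. If people with worse baseline pain or depression drop out more often, the first shows improvement that did not happen, and the second shows worsening that did not happen, because the remaining, milder participants regress toward the mean.

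The arm difference is distorted too if losses are unequal. Unequal losses are foreseeable: the Background names travel, weather, transport and health as obstacles to attending in person, and at-home delivery is meant to remove them.

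Treatment taken up after randomisation raises a related problem. It can be a consequence of the assigned arm or of poor response. Using it as a covariate or a ground for exclusion would depart from intention to treat.

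**Working it through.** The plan gives no power, SD, effect size or dropout rate, so it has no figure of its own to reproduce beyond 15 + 15 = 30.

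**Inputs.** From the documents: 15 per arm, two time points. Assumed: 3 or 4 of 15 lost (d = 0.20 or 0.267); dropouts' baseline worse than completers' by g = 0.5 to 0.9 SD; pre-post correlation ρ = 0.5 to 0.7; no true change; dropout depends on baseline only.

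**Formulas.** Completers' baseline mean lies d × g below that of all randomised. Their expected post mean lies ρ × d × g below it. Hence:

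- pre of all against post of completers: false improvement = ρ × d × g
- within-person change in completers: false worsening = (1 − ρ) × d × g

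| Lost | g (SD) | ρ | False improvement (pre of all, post of completers) | False worsening (completers' own change) |
|---|---|---|---|---|
| 3 of 15 | 0.5 | 0.5 | 0.050 | 0.050 |
| 3 of 15 | 0.5 | 0.7 | 0.070 | 0.030 |
| 3 of 15 | 0.9 | 0.5 | 0.090 | 0.090 |
| 3 of 15 | 0.9 | 0.7 | 0.126 | 0.054 |
| 4 of 15 | 0.5 | 0.5 | 0.067 | 0.067 |
| 4 of 15 | 0.5 | 0.7 | 0.093 | 0.040 |
| 4 of 15 | 0.9 | 0.5 | 0.120 | 0.120 |
| 4 of 15 | 0.9 | 0.7 | 0.168 | 0.072 |

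**Arm difference, 4 lost against 1.** Replace d by (4 − 1)/15 = 0.20, with the same g in both arms. The first reading gives 0.5 × 0.2 × 0.5 = 0.05 to 0.7 × 0.2 × 0.9 = 0.13 SD. The second gives 0.3 × 0.2 × 0.5 = 0.03 to 0.5 × 0.2 × 0.9 = 0.09 SD, in the opposite direction. With equal losses and equal gaps the difference is zero.

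**Simulation.** Drawing 15 per arm, with the chance of dropout rising with baseline, agrees with these formulas to within about 0.01 SD. Under the same conditions a common-baseline model is unbiased for both quantities. It also reduces the SD of the estimated arm difference by roughly 5 to 12%. With dropout unrelated to baseline, all the estimates centre on zero.

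**Scale.** In SD units, the standard error of an unadjusted difference in post means is √(2/15) = 0.37 at 15 per arm and √(2/12) = 0.41 at 12. Adjusted for baseline at 12 per arm it is about √((1 − ρ²) × 2/12), which is 0.29 at ρ = 0.7 and 0.35 at ρ = 0.5.

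**Treatment information.** In a large-sample regression with no true arm difference, adjusting for a post-randomisation treatment variable produced a false arm difference of about 0.18 to 0.50 SD. This assumed that the arm affects that variable and that the variable shares a cause with the outcome. When the arm did not affect the variable, the bias was about zero.

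**The case against.** A reader might infer that the plan has chosen to set pre means of everyone beside post means of completers. It does not say so. It never states who enters each time point, and its estimated changes could be within-person changes or come from a model using all available data.

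A reader might also infer that treatment changes after randomisation will be covariates or exclusions. The sentence mentions neither. It follows a request to keep psychotropic regimens stable, so description or monitoring is a natural reading. Scheduling a form at post-treatment is not the same as conditioning on it.

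Both objections stand: these are gaps in specification, not stated faulty methods.

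Three further points have force. First, the sizes come from assumptions, and the plan gives no margin or target difference against which a bias of 0.1 SD could be called important. Second, the bias is well below the sampling error, formal inference is disclaimed, and the hypothesis labelled primary is treatment satisfaction, which is measured only after treatment. Third, with two time points and a common baseline, participants with only a baseline score add nothing to the point estimate of the arm difference, which equals the baseline-adjusted estimate in completers.

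The third point does not defeat the remedy. The protection for the arm difference comes from adjusting for baseline, which neither simple reading does. For within-arm change, the dropouts' baseline scores do contribute.

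**Conclusion.** The point holds as a specification gap for which a better method is readily available. The plan names intention to treat and expects attrition, but does not make the principle operational. The plain readings of its text leave a bias of roughly 0.03 to 0.17 SD in within-arm change (3 or 4 of 15 lost) and roughly 0.03 to 0.13 SD in the arm difference (4 against 1 lost).

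These sizes rest on an assumed baseline gap of 0.5 to 0.9 SD and an assumed pre-post correlation of 0.5 to 0.7. They halve if the gap halves, and vanish if dropout is unrelated to baseline. The arm-difference part cancels if dropout acts alike in both arms.

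The documents do not support saying that intention to treat is contradicted. That would follow only if post-randomisation treatment information were used for adjustment or exclusion, which is left open but not stated. The matter deserves a change because the effect sizes are meant to guide a later trial and the remedy is cheap. It is a modest improvement to secondary, non-inferential estimates.

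**What to change.** Add a short paragraph to the statistical plan:

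- For BPI-SF and BDI-II (optionally PEG and PROMIS-PI), estimate change and arm difference with a common-baseline model of both time points that includes every randomised participant. For the arm difference this is equivalent to adjusting the post score for baseline. Report 95% intervals and the number contributing at each time point.
- Tabulate baseline values by arm for participants with and without post data.
- State that treatment information collected after randomisation is tabulated by arm only, and is not used as a covariate or for exclusion.

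The cost is one standard model per measure and one table, with no new data. The model assumes that missingness is at random given baseline; the baseline table shows how far completers and dropouts differ but cannot verify that assumption. The estimates remain imprecise, with a standard error of about 0.3 to 0.4 SD for the arm difference.
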